11.6 Clinical and Translational Research Laboratory (CTRL)

All samples will be processed by the Massey Cancer Center CTRL, the CTRL should be notified at least 1 day in advance.

CTRL Contact Information (For specimen collection, processing, storage, and transportation questions):

11.7 Sample Analysis

Samples will be stored by the CTRL and evaluated for biomarkers such as C-reactive protein, pro-inflammatory cytokines including IL-1 receptor antagonist, IL-6 ([31](#)), plasma citrulline and gene polymorphisms.

12 STUDY CALENDAR

Item	Eligibility ¹	Baseline (Prior to start of RT)	Every 2 weeks (\pm 4 days) through RT (for RT durations \geq 3 weeks) and at the completion of RT(\pm 4 days) ²	2 weeks (\pm 4 days) post- RT	8 weeks (\pm 4 days) post- RT
History & physical exam ³	x	x	x	x	x
ESAS scale		x	x	x	x
ECOG scale		x	x	x	x
PROMIS scale		x	x	x	x
Hemoglobin	x				
Creatinine	x				
TSH	x ⁴				
Ca	x ⁵				
CBC	x				
Albumin	x ⁵				
Bilirubin, ALT, AST	x				
AE assessment		x	x	x	x
FACIT-F, FACIT-Fatigue		x	x	x	x
Blood collection for biomarker studies (plasma)		x ⁶	x ⁶	x ⁶	x ⁶
Optional blood collection for gene polymorphism studies (PBMCs)		x ⁷			

¹Required within 28 days preceding the beginning of therapy.

²Patients who have both a 2-week follow-up visit and an end-of-RT visit within a 5-day window will have an end-of-RT visit only.

³May be performed by a mid-level provider.

⁴Only required if hypothyroidism is suspected.

⁵Only required if hypercalcemia is suspected.

⁶Draw peripheral blood into one EDTA or sodium heparin collection tube (1 x 6 mL).

⁷For patients who consent to the optional gene polymorphism studies, draw peripheral blood into one EDTA or sodium heparin collection tube (1 x 10 mL).

13 STATISTICAL CONSIDERATIONS

13.1 Study Design and Analysis

This is a double-blind, placebo-controlled trial randomizing participants to 20 mg oral melatonin at night throughout the course of their RT plus an additional 2 weeks. Eligible patients will be electronically randomized on a 1:1 ratio within each stratum to melatonin treatment or placebo. Investigational pharmacists will dispense either melatonin or placebo capsules according to a computer-generated random assignment list. The allocation scheme would keep the allocation ratio approximately equal across all of the strata. Stratification is done according to treatment duration (less than 3 weeks; equal to or greater than 3 weeks) and prior chemotherapy (yes/no). Treatment allocation will be concealed from patients, investigators, and study coordinators enrolling the participants. The statistical collaborator will be unblinded and provide the randomization list to the pharmacy. Interim results needed for Data and Safety Monitoring Committee (DSMC) review will be provided by the research nurse in a blinded manner; however, the statistician can unblind groups to the DSMC if there is a concern. The primary investigators and other collaborators would remain blinded.

The primary hypothesis of no change in fatigue will be tested using the ANOVA F-test after adjusting for duration of RT (binary) and prior chemotherapy. Stratified randomization will be used to keep the groups balanced; however, statistical model will also be adjusting for them. The final hypothesis test level will be adjusted using O'Brien Fleming spending function for type I error. Details of interim analysis are provided in [Section 13.6](#).

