8.6 Expedited Reporting Procedures for SAEs and UPs

Expedited Reporting Requirements (Events, Report Recipients, and Time Frames)		
SAEs	UPs	SARs
Sponsor-Investigator ¹ [name] 	Sponsor-Investigator ¹ [name]  .org	FDA ³
	DSMC ¹ 	
	IRB ²	

¹ Report event within 2 business days of becoming aware of the occurrence.

² Each UP must be reported to the VCU IRB within 5 business days of becoming aware of the occurrence.

³ The sponsor-investigator will report to the FDA any:

- SARs that are both serious and unexpected within 15 days of determining that the information is reportable.
- clinically important increase in the rate of SSARs within 15 days of determining that the information is reportable.
- unexpected fatal or life-threatening SARs within 7 days of receipt of the information.

[REDACTED]

[REDACTED]

[REDACTED]

[REDACTED]

[figure not shown]
[REDACTED]

[REDACTED]	[REDACTED]	[REDACTED]	[REDACTED]
[REDACTED]	[REDACTED]	[REDACTED]	[REDACTED]
[REDACTED]	[REDACTED]	[REDACTED]	[REDACTED]
[REDACTED]	[REDACTED]	[REDACTED]	[REDACTED]
[REDACTED]	[REDACTED]	[REDACTED]	[REDACTED]

[REDACTED]

The figure consists of a series of horizontal black bars of varying lengths, followed by a table with four rows and four columns of black and white cells.

■	■	■	■
■	■	■	■
■	■	■	■
■	■	■	■

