13.6 Interim Analysis

An interim analysis will be performed once one-half of the target patient sample size is accrued and evaluable. The unified family method with $\rho=0.3$ (45) will be used as the spending function to determine the rejection boundary, which is a modified version of the O'Brien Fleming method. As computed by SAS proc Seqdesign, 36 evaluable patients in each arm will be needed to perform this analysis and a standardized absolute z value of 2.49 will be needed to reject the null hypothesis at the interim stage. To maintain a 5% level of significance, the final analysis will be done at the 0.037 level, which is equivalent to using an absolute z score of 2.02 for rejecting the null hypothesis. The sponsor-investigator will remain blinded to the interim analysis, although it will be made available to the DSMC.

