14.2.2 Data and Safety Monitoring Committee

The study will be reviewed by the MCC Data and Safety Monitoring Committee (DSMC) initially according to the risk level specified by the MCC Protocol Review and Monitoring Committee (PRMC) and then according to a schedule based on study status and quality indicators. The DSMC reviews reports of the sponsor-investigator/study team and the MCC Compliance Office focusing on data integrity and patient safety.

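### The DSMC's safety data arrive blinded and nobody is assigned to compare event rates by arm; a closed by-arm table from the already unblinded statistician would close the gap cheaply

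*Combined protocol and SAP*

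**What the plan says.** Four parts of the combined protocol and SAP bear on this.

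- **Section 13.1, flow of data to the DSMC.** "Interim results needed for Data and Safety Monitoring Committee (DSMC) review will be provided by the research nurse in a blinded manner". The same sentence goes on to say that "the statistician can unblind groups to the DSMC if there is a concern". What counts as a concern is not defined.
- **Section 13.1, who knows the allocation.** "The statistical collaborator will be unblinded and provide the randomization list to the pharmacy". By contrast, "The primary investigators and other collaborators would remain blinded". No duty to tabulate adverse events by arm is given to the statistician or to anyone else.
- **Section 8.6, footnote 3.** "The sponsor-investigator will report to the FDA any" of several listed items, one being a "clinically important increase in the rate of SSARs within 15 days of determining that the information is reportable". In the table above that footnote, expedited SAE reports go to the sponsor-investigator; the DSMC is listed only under unanticipated problems (UPs).
- **Sections 14.2.2 and 13.6.** "The DSMC reviews reports of the sponsor-investigator/study team and the MCC Compliance Office focusing on data integrity and patient safety". The one planned interim comparison concerns fatigue: "a standardized absolute z value of 2.49 will be needed to reject the null hypothesis at the interim stage". Its result goes to the DSMC, and the sponsor-investigator stays blinded to it.

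**The concern.** The unblinding clause in section 13.1 is close to circular. The arms are opened when a concern arises, but a concern about one arm is hard to form from data that do not show the arms. The difficulty is greatest for effects expected in this population anyway. Section 8.2 lists daytime sleepiness and headache as likely with melatonin, and tiredness as likely with breast radiotherapy. A blinded assessor can put a drug effect down to radiotherapy. That attribution then decides whether the event counts as a suspected adverse reaction (8.1.2) and whether the individual stops in section 7.1 apply.

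The SSAR-rate duty in section 8.6 has a related problem. It asks for a judgement about a rate from someone who cannot see rates by arm, and nobody who can see them is told to look.

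What is at stake is how promptly an imbalance would be recognised by the one body placed to act on it.

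**Working it through.** **Step 1: the passages side by side.**

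| Task | Who has it | Can that party compare arms? |
|---|---|---|
| Supply DSMC review data (13.1) | research nurse, in blinded form | not described as holding the allocation |
| Review patient safety (14.2.2) | DSMC, from study-team and Compliance Office reports | only if unblinded on a concern (13.1) |
| Report a rise in the SSAR rate (8.6, footnote 3) | sponsor-investigator | no (13.1; blinded at the interim too, 13.6) |
| Hold the allocation (13.1) | statistician | yes, but no by-arm safety task is assigned |

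The only party able to make the comparison has no instruction to make it.

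**Step 2: illustration of size.** The plan states no figure for this point, so there is none to reproduce. Its interim size is 36 per arm (13.6), which is half of 71 (13.3) rounded up: 71/2 = 35.5. All event rates below are assumptions.

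Expected counts are n × p per arm; the pooled rate is (p_placebo + p_melatonin)/2.

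- 2% v 10%: 36 × 0.02 = 0.72 and 36 × 0.10 = 3.6; pooled (0.02 + 0.10)/2 = 6%.
- 5% v 20%: 36 × 0.05 = 1.8 and 36 × 0.20 = 7.2; pooled (0.05 + 0.20)/2 = 12.5%.
- 10% v 25%: 36 × 0.10 = 3.6 and 36 × 0.25 = 9.0; pooled (0.10 + 0.25)/2 = 17.5%.

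**Step 3: chance that a count stands out.** For a background rate p0, take the smallest k with P(X ≥ k | p0) ≤ 5%. For one arm, X is binomial with n = 36; for the pooled report, n = 72. Then find the probability of reaching k under the assumed rates. The last column is a one-sided 5% Fisher comparison of the two arms. These are yardsticks for comparing reports and are not proposed as rules.

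| Placebo v melatonin | Background taken as | Melatonin-arm count (k of 36) | Pooled count (k of 72) | Fisher, arm v arm |
|---|---|---|---|---|
| 2% v 10% | 2% (true) | 71% (3) | 44% (5) | 17% |
| | 4% (double) | 29% (5) | 14% (7) | 17% |
| 5% v 20% | 5% (true) | 87% (5) | 70% (8) | 47% |
| | 10% (double) | 43% (8) | 10% (13) | 47% |
| 10% v 25% | 10% (true) | 71% (8) | 50% (13) | 40% |
| | 20% (double) | 17% (12) | 1% (21) | 40% |

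**Step 4: reading it.** With the same assumed background, the melatonin-arm count stands out more often than the pooled count in every row. The pooled count depends heavily on knowing the background, and the plan gives none for serious or grade 3 and higher related events. The direct comparison needs no background, because the placebo arm supplies it. It is not always the more sensitive: at 2% v 10% it flags 17%, against 44% for a pooled count with the background known exactly. A by-arm table's firm advantages are that it shows which arm the events are in and brings its own comparator.

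**The case against.** The strongest reply is that monitoring is not blind in any strong sense.

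- Section 13.1 never says that the data are pooled. Unblinding groups could mean revealing the identity of coded arms, in which case an imbalance would be visible and could itself raise the concern. This reading is possible. It is the less natural one, since the nurse who supplies the data is not described as holding the list needed to split them. The wording needs settling either way.
- The UP definition in 8.1.5 includes unexpected frequency, and UPs reach the DSMC within 2 business days (8.6). This is a second aggregate route, and it stands. It has no comparator by arm, and blinded staff apply it.
- The statistician is unblinded throughout and meets the study team at least quarterly; the team reviews whether further enrolment is appropriate (14.1). The DSMC receives the interim, which is two-sided on a fatigue subscale that includes tiredness and daytime sleep. All of this stands.
- The background in 1.2.3 presents melatonin as low risk, and 20 mg as comparable to placebo for side effects. That lowers the urgency.

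A reader might infer that an imbalance would first come to light at the final analysis, after all 142 patients had been treated. The documents do not support that, because the routes above stay open. A reader might also infer that no safety trigger of any kind exists and that one must be written. The visible text has no count or rate that pauses the study, but the DSMC's own operating rules are not among the documents, and whether a threshold is needed is a matter for the DSMC and sponsor. Nor does the 17.5% pooled figure show masking if it is applied to daytime sleepiness: 25% in the melatonin arm alone would equally fit the likely category in 8.2.1 (10% or more).

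**Conclusion.** The concern holds in a limited form. As written, the DSMC's routine data most naturally do not separate the arms, the condition for opening them is undefined and hard to meet from such data, and no one is assigned a by-arm comparison. The SSAR-rate duty in 8.6 and the blinding in 13.1 do not strictly contradict each other, since the statistician or DSMC could inform the sponsor-investigator; but no text says that they do, and the passages must be reconciled.

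The consequence is a risk of late recognition of an imbalance between arms. Its size cannot be derived from the documents. Under the assumed rates, a melatonin-arm count at 36 patients stands out 71% to 87% of the time and a pooled count 44% to 70% if the background is known; the ranges fall to 17% to 43% and 1% to 14% if the background is taken at double its true value.

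The conclusion assumes that blinded means not split by arm, and it covers the visible text. Parts of the protocol are redacted, but sections 7, 8.3 to 8.6, 13 and 14, where such provisions would belong, are readable. Label: cheap improvement.

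**What to change.** 1. In sections 13.1 and 14.2.2, state that at each scheduled DSMC review, and at the section 13.6 interim, the already unblinded statistician gives the DSMC alone a closed table by arm of AEs, SAEs and SSARs, and discontinuations of study drug under section 7.1. This replaces dependence on an undefined concern and settles what blinded form means for the nurse's report.
2. In section 8.6, footnote 3, assign the by-arm check of the SSAR rate to that statistician and the DSMC, who inform the sponsor-investigator when an increase is reportable.

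No safety threshold or stopping rule is proposed here.

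The cost is protocol wording and one extra table per existing review, with existing staff and committee. The downside is that the DSMC sees safety data by arm earlier than it otherwise would; investigators stay blinded.

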13.2 Patient Replacement

Patients (on either the melatonin treatment or placebo arm of the study) who are not evaluable for the primary endpoint because they drop out or are removed from the study prior to completing the FACIT-Fatigue subscale at the completion (± 4 days) of RT will be replaced.

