5.2 Study Withdrawal Procedures

5.2.1 A patient may decide to withdraw from the study at any time.

5.2.2 A patient may be removed from treatment for one of the following criteria:

5.2.2.1 If in the opinion of the treating physician, it is in the best interest of the patient to do so.

5.2.2.2 Sponsor-investigator's decision to discontinue the study.

5.2.3 The reason for withdrawal from the study and the date the patient was removed from the study must be documented in the case report form.

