6.7 Follow-Up Period

Patients will be followed for 8 weeks (\pm 4 days) after completion of RT or until death, whichever occurs first. Patients removed from the study treatment for unacceptable AEs will be followed until resolution or stabilization of the AE.

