13.3 Sample Size/Accrual Rates

The primary endpoint of the study is the change in FACIT-F score for patients receiving melatonin and the same for patients receiving placebo. In a prior study of a pharmacological intervention for cancer-related fatigue ([44](#)), the expected mean and SD of the overall change in FACIT-F score in the placebo group was 13 and SD was 14.78. We assume the same SD for the melatonin subgroup and a clinically meaningful difference is deemed to be a half SD difference which is approximately 7 units. Based on these findings and using a two-sided t-test at 5% level of significance, we would need 71 patients in each of the placebo and melatonin groups for 80% power. Our target cohort size is, therefore, 142 patients.

Compliance is expected to be very high, and the drop-out rate is expected to be minimal. As a result, no adjustment of the sample size is done to accommodate drop outs or lack of compliance; however, the patients dropping out before the completion of the post treatment questionnaire will be replaced.

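### Patients who leave before the end-of-RT FACIT-Fatigue score are replaced and no all-randomised analysis is named, so both looks in effect compare completers; the bias is small if dropout is minimal, as the plan expects

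*Combined protocol and SAP*

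**What the plan says.** Section 13.2 (Patient Replacement) replaces patients in either arm "who are not evaluable for the primary endpoint because they drop out or are removed from the study prior to completing the FACIT-Fatigue subscale" at completion of RT, within a window of 4 days either side. Section 13.3 says it again: "the patients dropping out before the completion of the post treatment questionnaire will be replaced". It makes no allowance for loss in the sample size, because "the drop-out rate is expected to be minimal", and gives no rate.

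Section 13.6 counts the interim in the same currency: "36 evaluable patients in each arm will be needed to perform this analysis". Section 13.1 says the primary hypothesis will be "tested using the ANOVA F-test after adjusting for duration of RT (binary) and prior chemotherapy". Neither these sections nor Section 13.5 nor the Protocol Summary defines an all-randomised analysis set, a method for missing scores, or a sensitivity analysis. The mention of the overall cohort in Section 13.5 concerns other secondary outcomes and does not fill the gap.

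Three other places bear on the point:

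- Section 5.2.3, on what the case report form must hold: "The reason for withdrawal from the study and the date the patient was removed from the study must be documented". No analysis of these data by arm is planned.
- Section 6.7: patients are followed for 8 weeks "after completion of RT or until death, whichever occurs first".
- Section 12 (Study Calendar): the row "FACIT-F, FACIT-Fatigue" is marked at baseline, every 2 weeks during RT for courses of 3 weeks or more, at the end of RT, and at 2 and 8 weeks afterwards.

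**The concern.** Randomisation protects the comparison of everyone who was randomised. A patient who leaves before the end of RT has no end-of-RT value, so an ANOVA on change from baseline to that visit cannot use her. Enrolling another patient in her place brings the count back to target, but it does not bring back her outcome. Patients who stay on study but miss that questionnaire fall outside the replacement rule, and no other rule covers them.

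Bias arises if leaving is related to fatigue and the rates, or the leavers' differences, are unequal across arms. The direction is not known in advance. If leavers are more fatigued than the rest of their arm, the arm that loses more of them looks better than it is. The interim is counted the same way, so an early rejection could be affected as well as the final result.

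The documents show a possible route, though not a demonstrated one. Section 8.2.1 lists daytime sleepiness as likely with melatonin, Section 7.1 has patients stop study drug for certain related adverse events, and the FACIT-Fatigue subscale in Appendix 1 includes an item on needing daytime sleep.

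**Working it through.** **1. The plan's own figure.** Inputs from Section 13.3: difference 7, SD 14.78, two-sided 5%, 80% power. A two-sample t-test calculation gives 70.96, rounded up to 71 per arm, with power 80.0% at 71. The stated size reproduces. With no dropout allowance and replacement of leavers, 142 is a count of patients with the score, not of patients randomised. If 2%, 5% or 10% of all patients left (assumed), 142/(1 − d) gives 145, 150 or 158 randomised, so 3, 8 or 16 patients would have no stated place in the primary comparison.

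**2. Size of the shift.** Suppose a fraction d of one arm leaves, none of the other does, and leavers lie g SDs below their arm's overall mean. The completers' mean in that arm then exceeds the arm's mean by

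shift = d/(1 − d) × g × 14.78.

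For example, d = 0.10 and g = 1 give 0.1111 × 14.78 = 1.64 units. Both d and g are assumptions; the documents give neither.

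**3. Effect on the two-look test.** The boundaries are those in Section 13.6 (|z| of 2.49 at 36 per arm, 2.02 at the end), with 71 per arm at the end because replacement restores N. Standard errors are 14.78 × √(2/36) = 3.48 and 14.78 × √(2/71) = 2.48, and the correlation between looks is √(36/71) = 0.71. The normal approximation is used. With no shift, type I error is 4.99% and the chance of rejecting at a true difference of 7 is 79%.

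| Excess dropout in one arm | Leavers worse by | Shift (units) | Share of 7 | Type I error | Rejection at a true 7 (shift against / for the effect) |
|---|---|---|---|---|---|
| 2% | 0.5 SD | 0.15 | 2% | 5.0% | 78% / 81% |
| 5% | 0.5 SD | 0.39 | 6% | 5.3% | 75% / 84% |
| 10% | 0.5 SD | 0.82 | 12% | 6.2% | 69% / 88% |
| 2% | 1 SD | 0.30 | 4% | 5.2% | 76% / 83% |
| 5% | 1 SD | 0.78 | 11% | 6.1% | 70% / 87% |
| 10% | 1 SD | 1.64 | 23% | 9.9% | 57% / 93% |

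With loss in both arms, the shifts subtract. At 10% versus 5% and g = 1, the net shift is (0.1111 − 0.0526) × 14.78 = 0.86 units. With equal rates and equal gaps it is zero.

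**4. How much a model recovers.** In a simulation, leaving depended directly on the end-of-RT score (logistic, assumed slope 1 per SD) and the estimate used one mid-RT score under a missing-at-random assumption. About 85%, 66% and 36% of the completer shift remained at assumed mid-to-end correlations of 0.4, 0.6 and 0.8. This is an unfavourable case for the model, because leaving depends on the score that is never seen.

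**The case against.** The strongest reply is that the problem is negligible on the plan's own premise. Section 13.3 expects minimal dropout and very high compliance. The trial is double-blind, and Section 1.2.3 reports side effects at 20 mg comparable to placebo in an earlier trial in advanced cancer, so unequal loss is not the natural expectation. The largest figures in the table need 10% loss in one arm, none in the other, and leavers a full SD worse. This stands, and it limits the weight of the point. But these are expectations, with no rate attached and no planned check by arm.

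A reader might infer that the plan restricts the analysis to completers. It does not say so. Section 13.2 is an enrolment rule and never states that replaced patients are excluded. The completer comparison is an inference from three things together: the replacement rule, the count of evaluable patients, and a test that cannot use a patient without the end-of-RT score.

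A reader might also infer that stopping study drug loses the primary score. The documents do not support that. Section 7.1 speaks of discontinuing treatment, Section 13.2 of leaving the study. Section 6.7 continues follow-up, and the calendar does not make FACIT depend on taking drug. On the other side, Section 5.2 lists removal from treatment under study withdrawal, and for patients removed for adverse events Section 6.7 mentions only following the event. The visible text leaves this open, and because Section 6.2 is blacked out, its silence cannot be held against the plan.

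Finally, a repeated-measures model recovers only part of the bias if leaving depends on the unseen score. That is correct, and it is why a missing-not-at-random analysis has to accompany it.

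**Conclusion.** The point holds as an analysis choice that should be changed, with medium confidence. Followed as written, the replacement rule and the ANOVA give a comparison of patients with an end-of-RT score at both looks, and patients who stay on study but miss the questionnaire have no stated handling.

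Bias needs loss that is related to fatigue and differs between arms, in rate or in the leavers' gap. In the range nearest to the plan's expectation (2% excess in one arm, leavers 0.5 to 1 SD worse), it is a small fraction of the 7-unit target and type I error hardly moves. It becomes material only towards 10% excess. All of these sizes rest on assumed dropout and gaps, and on the plan's SD of 14.78.

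The documents do not support the stronger conclusions that the result will be biased or that type I error is near 10%. Nor is the sample size wrong on this account.

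**What to change.** - **Analysis set.** Define the primary set as all randomised patients in their assigned arm, including those who are replaced and those who miss the end-of-RT questionnaire. At the interim, include every randomised patient whose end-of-RT window has passed; the 36 evaluable per arm can remain the trigger. Replacements may still be enrolled.
- **Primary estimate.** Keep the end-of-RT contrast. Estimate it with a likelihood-based repeated-measures model using baseline, both stratification factors and the FACIT-Fatigue scores already in the calendar. Entering baseline as one of the responses lets a patient with only a baseline score contribute.
- **Sensitivity analyses.** Keep the completer ANOVA as one. Add one delta-adjusted (missing-not-at-random) analysis with the shifts fixed in advance; the 0.5 and 1 SD used above are a possible range, applied by arm.
- **Reporting.** Tabulate dropout and reasons by arm from the data recorded under Section 5.2.3.
- **Clarification.** Confirm in the protocol that scheduled FACIT assessments continue after study drug is stopped.

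The cost is analysis-plan text and somewhat more analysis work, with no new visits or questionnaires. The downside is reliance on a missing-at-random assumption. It is weakest for RT courses under 3 weeks, which have no FACIT between baseline and the end of RT. The model reduces the bias but does not remove it if leaving depends on the unseen score.
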